7. STUDY CALENDAR

Baseline evaluations are to be conducted within 6-weeks prior to start of protocol therapy. Scans must be done ≤ 12 weeks prior to the start of chemotherapy if delivered or radiation therapy if no chemotherapy is delivered. In the event that the participant's clinical condition is deteriorating, laboratory evaluations should be repeated within 48 hours.

Tests and Observations	Pre-study	During Radiation	Follow Up (1)
Informed Consent and registration	X		
Pathology Review (DF/HCC)	X		
Medical History	X		
Physical Exam	X		X
Echocardiogram (2)	X		X(2)
Imaging	X (3)		As clinically indicated
Toxicity/AE Assessment		X weekly	X
Data Sheets			X (4)
Labs (5)	X		X
Optional Photography	X	X	X

Notes:

(1) Follow up schedule is at 4 weeks and 2 months, and 6 months after treatment, then at 12 months and annually to five years after treatment. Labs are only collected at the first two follow up visits (4 weeks and 2 months). Visit window for follow up is +/- 3 weeks for the 4week and 8 week follow up visits, then +/- 6months for the 6month and annual visits.

(2) Echocardiogram including Strain echocardiogram will be performed for all patients. Echocardiogram data will be collected prior to radiation therapy (or within first week of treatment), at 4 weeks after completion of radiation therapy, and 2 months after radiation therapy. Conventional two-dimensional (2D) and Doppler echocardiography will be obtained in standard views. Tissue Doppler imaging will be acquired using standard views. Imaging parameters will be optimized and the frame rate will be set greater than 150 frames/sec for acquisition of tissue Doppler imaging. Echocardiographic loops of at least 3 beats will be recorded. Echocardiograms will be read in the conventional manner and reported in the subject's medical record. TDI-derived parameters, such as myocardial velocities, strain, strain rate and torsion, will be analyzed offline using customized computer software (EchoPac, GE Healthcare, Milwaukee, WI).

(3) Diagnostic imaging required pre-study:

- Baseline mammography prior to surgery
- For patients with lymphatic involvement Computed Tomography (CT) scan of the chest, CT of the abdomen, and bone scan and/or Positron Emission Tomography (PET)/CT scan are required. For patients with low burden nodal disease, these scans are not required.

(4) The Patient Evaluation form and the Physician Data Therapy forms will be considered optional with the intent to complete at all follow up study timepoints and missed forms will not be considered as constituting protocol deviations or violations.

(5) Standard clinical labs including CBC with differential; TSH at baseline; Biomarkers will be assessed only at the times of echocardiography. Approximately 5 cc of blood will be taken for each measurement of BNP and NTproBNP, and 5 cc of blood for ultrasensitive troponin. Blood will be spun at 3000 rpms for 10 minutes, the plasma will be aliquotted into daughter tubes and stored at -80. BNP levels will be measured with a twosite dual-monoclonal immunochemiluminescent assay (ADVIA Centaur® BNP, Bayer Diagnostics, Tarrytown, NY) using the ADVIA Centaur immunoassay system. NT-proBNP levels will be measured with an electrochemiluminescence

CONFIDENTIAL

This document is confidential. Do not disclose or use except as authorized.

sandwich immunoassay (Elecsys® ProBNP, Roche Diagnostics Inc, Indianapolis, IN) using the Roche 2010 system. For non acutely dyspnic subjects aged <75 years of age, the upper limit of normal is considered 125 pg/ml (manufacturers recommendations). Troponin I will be measured using a new generation technique that has shown increased sensitivity compared to routine measurements (Architect STAT troponin assay, Abbot Diagnostics). Labs will be performed in conjunction with routine labs obtained pre- and post- treatment only at 3 time points, prior to radiation therapy, 4 weeks after radiation therapy, and 2 months after radiation therapy.

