cardiac events.²⁷ Doses of 25 Gy have been shown to induce temporary perfusion defects and ≥ 5 -6% of the heart receiving ≥ 25 -27 Gy has been accepted by some to define “unfavorable cardiac anatomy” based on correlation of this heart volume to the Stockholm trial for patients with left sided tumors that showed a high rate of cardiac morbidity and mortality.^{15, 21-22, 28-29} There is emerging data that doses to specific parts of the heart, such as the coronary arteries, may be more important in predicting cardiac outcomes.³⁰ Strain echocardiogram has recently shown promise as an accurate and relatively inexpensive study to determine myocardial abnormalities in the left ventricle for doses > 3 Gy immediately post radiation and at 2 months following radiation.³¹ Control patients receiving right sided radiation did not show any changes on post radiation studies. Pericarditis is a very rare toxicity, occurring in $<1\%$ of patients, but may lead to hospitalization.³² In addition, the increased use of cardiotoxic chemotherapy over the past several years adds yet another confounding factor to determining the effect of radiation therapy on cardiac outcomes. Doxorubicin and Herceptin, particularly when used in combination, are known to increase the risk of cardiac disease.³³⁻³⁴ These agents were not included in the chemotherapeutic regimens used in the aforementioned trials. Currently, Doxorubicin and Herceptin are both included in standard chemotherapeutic regimens and are often administered in combination.³⁵ It is not fully known how radiation therapy in the setting of these agents will affect cardiovascular outcomes. Maximal cardiac sparing achieved through proton therapy has the potential to decrease this risk by decreasing mean heart dose as well as volume receiving 40 Gy and 25 Gy (Figure 2 & 3).

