The following retrospective studies report on incidences of RP after adjuvant radiation for breast cancer. It is important to note that only two of the series included patients who required internal mammary lymph nodes.^{37, 39} Voduc reported a 2% incidence of grade 2-3 RP using the RTOG scale in a group of 77 women with breast cancer treated at the British Columbia Cancer Agency (BCCA). No grade 4 or 5 events occurred. All patients had lymph node–positive disease with negative estrogen receptor expression and underwent surgery, adjuvant doxorubicin/cyclophosphamide for four cycles followed by four cycles of paclitaxel (AC,T) followed by radiation therapy. This study represents a patient population who were treated with the systemic regimen that most of these patients in the proposed study will receive. Yu and Buchholz reported the MD Anderson Cancer Center (MDACC) incidence of RP in a Phase III study comparing neoadjuvant four cycles of paclitaxel followed by four cycles of 5-fluorouracil, doxorubicin, cyclophosphamide (FAC) versus eight cycles of FAC.³³ Of 524 patients treated in the study, 189 also received radiation therapy. RP was scored using the RTOG scale. Clinically evident pneumonitis was observed in 5% of the paclitaxel-FAC group and 4.5% of the FAC-only group (difference not significant). Only two patients of 189 required steroids, one other required narcotics, and none were hospitalized. Taghian et al. from the Massachusetts General Hospital (MGH) reported RP rates in 41 breast cancer patients treated with mastectomy and axillary lymph node dissection followed by four cycles of adjuvant doxorubicin/cyclophosphamide followed by four cycles of paclitaxel.³⁹ Radiation therapy to the chest wall and regional lymphatics was given concurrently with paclitaxel in 21 patients and sequentially in the remainder. In contrast to the BCCA and MDACC experiences, an incidence of 14.6% (6 of 41 patients) grade 2-3 RP using the RTOG scale was observed at the MGH regardless of the sequencing. Five of the events were grade 3 and no grade 4-5 events occurred. Lind et al reviewed Duke’s experience with RP in a cohort of breast cancer patients treated with breast-only radiation therapy versus comprehensive radiation therapy.³⁷ In 319 patients who received radiation to the breast alone the RP rate was 0.9%. When comprehensive radiation therapy was employed, the RP incidence increased to 4.1% (12 of 294 patients). All 12 patients were

CONFIDENTIAL

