5.2.2 Timing of the radiation therapy

CONFIDENTIAL

This document is confidential. Do not disclose or use except as authorized.

Radiation therapy should be initiated no later than 20 weeks following chemotherapy and surgery. Surgery can exceed 20 weeks if the patient undergoes chemotherapy following surgery. Radiation should not be started earlier than 3 weeks following Taxane based chemotherapy.

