5.3 General Concomitant Medication and Supportive Care Guidelines

Concomitant chemotherapy as dictated by protocol or the treating physician is allowed. All appropriate non-investigational supportive care medications or treatments may be used for optimal symptom management.

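### The cardiac baseline may be taken before the last chemotherapy dose, so for some patients the pre/post-radiation change in strain can mix a chemotherapy effect with a radiation effect

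*Combined protocol and SAP*

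**What the plan says.** The general baseline rule in Section 7 is "Baseline evaluations are to be conducted within 6-weeks prior to start of protocol therapy". The pre-study column of the calendar includes the echocardiogram and the labs.

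The echocardiogram note in the same section says "Echocardiogram data will be collected prior to radiation therapy (or within first week of treatment), at 4 weeks after completion of radiation therapy", with a further study at 2 months. It sets no earliest date and does not mention chemotherapy. Section 5.1.2 has the same gap. For blood, note 5 says "Biomarkers will be assessed only at the times of echocardiography".

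On the gap before radiation, Section 5.2.2 says "Radiation should not be started earlier than 3 weeks following Taxane based chemotherapy". It gives no minimum for other agents. The upper limit is "Radiation therapy should be initiated no later than 20 weeks following chemotherapy and surgery". Section 5.3 adds "Concomitant chemotherapy as dictated by protocol or the treating physician is allowed".

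On systemic treatment, Section 2.2 describes a published series given doxorubicin/cyclophosphamide, then paclitaxel, then radiation, and calls this "the systemic regimen that most of these patients in the proposed study will receive". The same section treats cardiotoxic chemotherapy as a confounder of radiation's cardiac effect: "Doxorubicin and Herceptin, particularly when used in combination, are known to increase the risk of cardiac disease".

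Objective 1.3.1 asks for early cardiac effects of radiation by strain echocardiography. Section 12.2.3 tests this with ANOVA contrasts across one pre-radiation and two post-radiation measurements. Fixed effects for subgroups are optional there, and the only example given is dose level.

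**The concern.** The comparison is within patient and no cohort goes without radiation, so the baseline carries the whole inference about cardiac effects. If the baseline comes before the last chemotherapy dose, anything that dose does to myocardial function lies between the two measurements being compared. A decline caused by chemotherapy would then count as a radiation effect. Recovery from a depression present during chemotherapy would offset a real radiation effect.

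Section 7 already ties the timing of the diagnostic scans to the start of chemotherapy, so a rule of this kind is familiar to the plan. The cardiac baseline lacks one.

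**Working it through.** The plan states no figure on this point, so there is nothing to reproduce. The check compares time windows and then gives an illustration on assumed inputs.

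**Step 1. Overlap.** Inputs: baseline window W = 6 weeks (Section 7); gap g from last chemotherapy dose to first fraction, at least 3 weeks after a taxane and at most 20 weeks (Section 5.2.2).

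Weeks of the window that precede the last dose = max(0, W - g).

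| g (weeks) | Overlap (weeks) | Share of 6-week window |
|---|---|---|
| 3 | 6 - 3 = 3 | 50% |
| 4 | 2 | 33% |
| 5 | 1 | 17% |
| 6 to 20 | 0 | 0% |

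For the echocardiogram the permitted period also includes the first week of treatment, so at g = 3 the share is 21/(42 + 7) = 21/49 = 43%. For a non-taxane agent no minimum gap is stated, so the formula alone allows an overlap of up to 6 weeks. If the echocardiogram note is read as replacing the 6-week rule, there is no earliest date at all.

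**Step 2. Which doses fall in the overlap.** In the sequence that Section 2.2 expects for most patients, paclitaxel comes last. The overlapped doses are then paclitaxel. The agents that Section 2.2 names as cardiotoxic are doxorubicin and Herceptin. Doxorubicin ends before the paclitaxel course, and the timing of Herceptin is not given.

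**Step 3. Share of patients affected (assumed).** Suppose baselines are spread evenly over the window and gaps evenly over 3 to 8 weeks. The mean overlap is (3 x 3/2)/5 = 0.9 weeks, so the share is 0.9/6 = 15%, or 0.9/7 = 13% with the first treatment week included. With gaps spread over 3 to 12 weeks, the mean overlap is 4.5/9 = 0.5 weeks and the share is 7-8%.

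**Step 4. Effect on the contrast (assumed).** Let f be the share affected and d the chemotherapy shift in SDs of the within-patient change, all in one direction. Bias = f x d. The standard error is 1/sqrt(n), which is 0.20 at n = 26 and 0.18 at n = 32 (the evaluable and accrual numbers per cohort). As a simplification of the ANOVA contrast, use a two-sided 5% one-sample t test on the change, with noncentrality f x d x sqrt(n) and no true radiation effect.

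| f | d | Bias (SD) | Rejection, n = 26 | Rejection, n = 32 |
|---|---|---|---|---|
| 0.15 | 0.3 | 0.045 | 5.6% | 5.7% |
| 0.15 | 0.5 | 0.075 | 6.6% | 7.0% |
| 0.25 | 0.3 | 0.075 | 6.6% | 7.0% |
| 0.50 | 0.5 | 0.25 | 23.2% | 27.8% |

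The last row needs both inputs at their extreme. With even baselines over 6 weeks, f = 0.50 means that every patient starts radiation at the 3-week minimum.

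**The case against.** The strongest reply is that the overlap is permitted but may be uncommon, and that the doses inside it may not matter. Both parts largely stand. Section 2.2 supports the regimen as typical, but not the timing: overlap also needs radiation to start within 6 weeks of the last dose and a baseline taken earlier than that gap. Nor do the documents say that a late paclitaxel dose moves strain or the biomarkers. A reader might infer that doxorubicin damage will typically be read as radiation damage. The documents do not support that, because in the expected sequence doxorubicin is finished before the overlap begins.

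A second reply is that the window is only one route. Chemotherapy during radiation is allowed, and delayed effects of earlier treatment can appear after any baseline. That also stands: a timing rule reduces the confounding but does not remove it.

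A third is that Section 12.2.3 already permits fixed effects for treatment factors. This gives little protection. The terms are optional, and a yes/no main effect is a between-patient term that does not adjust a within-patient change.

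Finally, Section 12 says accrual was adjusted partly for completeness of strain testing, so a narrower window has a real cost. It does, but the echocardiogram and blood sample are already planned, and only their timing would move.

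**Conclusion.** The concern holds in a limited form. Compliant baselines can precede the last chemotherapy dose, by up to 3 weeks after a taxane, and for those patients the pre/post change cannot be assigned to radiation alone. The overlap arithmetic needs no assumption beyond the two stated windows.

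The consequence cannot be sized from the documents. The 6-7% false-positive rate is an illustration that assumes 15% affected and a one-directional shift of 0.3-0.5 SD; shifts in opposite directions would partly cancel in the mean. A reader might infer a rate of 23-28%, but that takes the extreme of both assumed inputs. Nor does it follow that the data can never separate the two effects: if treatment dates are recorded, a contrast limited to patients without intervening cytotoxic treatment is possible.

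Strain is a descriptive secondary endpoint, and the two-stage feasibility rule in Section 12.1 is unaffected. For BNP, NT-proBNP and troponin the point concerns interpretation only, since Section 12.2 states no biomarker analysis.

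**What to change.** 1. In Sections 7, 5.1.2 and 5.1.5, require the baseline strain echocardiogram and biomarker sample to be taken after the last pre-radiation chemotherapy dose, within the existing window. This brings the overlap from pre-radiation chemotherapy to zero.
2. Record the date of the last pre-radiation dose and any concurrent systemic therapy, with agent and dates.
3. In Section 12.2.3, add a sensitivity pre/post contrast that excludes patients given cytotoxic treatment between baseline and the last measurement. If systemic-therapy terms are modelled, enter them as interactions with time, not as main effects.

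Cost: for a patient starting radiation 3 weeks after a taxane, the pre-radiation window falls from 6 weeks to 3, plus the first treatment week already allowed for the echocardiogram. A few more baselines will be out of window. For patients already enrolled, only the sensitivity analysis applies, where their chemotherapy dates are on record. No change to chemotherapy or radiation timing is proposed.

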6. EXPECTED TOXICITIES AND DOSING DELAYS/DOSE MODIFICATIONS

The CTEP Active Version of the NCI Common Terminology Criteria for Adverse Events (CTCAE) will be utilized for AE reporting. The CTEP Active Version of the CTCAE is identified and located on the CTEP website at

http://ctep.cancer.gov/protocolDevelopment/electronic_applications/ctc.htm
<https://phsexchweb.partners.org/exchweb/bin/redir.asp?URL=http://ctep.cancer.gov/protocolDevelopment/electronic_applications/ctc.htm>. All appropriate treatment areas should have access to a copy of the CTEP Active Version of CTCAE. If possible, symptoms should be managed symptomatically. In the case of toxicity, appropriate medical treatment should be used.

All radiation related grade 2 and greater adverse events experienced by participants will be collected from the time of the start of radiation and throughout the study and until the final study visit. Participants continuing to experience toxicity at the off study visit may be contacted for additional assessments until the toxicity has resolved or is deemed irreversible.

It is anticipated that toxicities will be decreased with proton radiation.

CONFIDENTIAL

This document is confidential. Do not disclose or use except as authorized.

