9. ADVERSE EVENT REPORTING REQUIREMENTS

9.1 General

CONFIDENTIAL

This document is confidential. Do not disclose or use except as authorized.

Adverse event collection and reporting is a routine part of every clinical trial. This study will use the descriptions and grading scales found in the CTEP Active Version of the NCI Common Terminology Criteria for Adverse Events (CTCAE) will be utilized for AE reporting. The CTEP Active Version of the CTCAE is identified and located on the CTEP website at

http://ctep.cancer.gov/protocolDevelopment/electronic_applications/ctc.htm
<https://phsexchweb.partners.org/exchweb/bin/redir.asp?URL=http://ctep.cancer.gov/protocolDevelopment/electronic_applications/ctc.htm>. All appropriate treatment areas should have access to a copy of the CTEP Active Version of CTCAE.

Information on all adverse events, whether reported by the participant, directly observed, or detected by physical examination, laboratory test or other means, will be collected, recorded, followed and reported as described in the following sections.

Adverse events experienced by participants will be collected and reported from initiation of study treatment, throughout the study, and within 30 days of the last dose of study treatment. Participants who experience an ongoing adverse event or related to study procedures and/or study treatment beyond 30 days will continue to be contacted by a member of the study team until the event is resolved, stabilized, or determined to be irreversible by the participating investigator.

Participants should be instructed to report any serious post-study event(s) that might reasonably be related to participation in this study. The investigator should notify the IRB and any other applicable regulatory agency of any unanticipated death or adverse event occurring after a participant has discontinued or terminated study participation that may reasonably be related to the study.

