9.3 Recording Adverse Events

Adverse event information will be obtained at each contact with the participant. All adverse events will be recorded on the appropriate study-specific case report forms (CRFs).

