12.2 Analysis of Secondary Endpoints

Secondary endpoints of this study will be analyzed as follows:

- 12.2.1 Exact binomial methods will be used to construct 95% confidence intervals for estimating the rates of acute, sub-acute and late toxicities during and after proton radiation to the left chest wall and regional draining lymphatics. The precision provided by a sample size of 26 patients is associated with a maximum half-width of 20%, but the 95% confidence intervals will be narrower in practice, as the observed toxicity rates are expected to be generally low. The same methods will also be used to analyze the post-radiation outcomes of breast reconstruction, including the rates of implant complication, contracture, infection, unplanned cosmetic surgeries.
- 12.2.2 Progression-free survival is defined as the duration from the start of radiation to the date of objective disease progression or death due to any cause, whichever is earlier. Progression-free survival will be estimated using Kaplan-Meier methodology. The 5-year

CONFIDENTIAL

This document is confidential. Do not disclose or use except as authorized.

progression-free survival rate will be reported and a 95% confidence interval for this rate will be calculated using Greenwood's formula. Patients who do not experience a progression and are still alive will be censored at their date of last contact.

- 12.2.3 Data from the strain echocardiogram will be analyzed for each parameter, including myocardial velocity, strain, strain rate and torsion. ANOVA methods will be used to analyze the pre- and two post-radiation measurements, using linear contrasts to test the significance of cardiac function changes over time. Fixed effects may be incorporated to explore subgroup differences defined by patient and treatment factors, for example, dose level.

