Remark: Fibrosis is usually a “late effect seen >3 months after radiation or combined modality therapy (including surgery). It is thought to represent scar/fibrotic tissue. It may be difficult to distinguish from pneumonitis that is generally seen within 3 months of radiation or combined modality therapy.

CONFIDENTIAL

This document is confidential. Do not disclose or use except as authorized.

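### The 6-month visit window runs from month 0 to month 12, so a compliant patient can go unassessed through months 3 to 12, which weakens capture of transient and mild late findings

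*Combined protocol and SAP*

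**What the plan says.** Section 7 (Study Calendar), note 1, sets the schedule: "Follow up schedule is at 4 weeks and 2 months, and 6 months after treatment, then at 12 months" and yearly to five years. It continues "Visit window for follow up is +/- 3 weeks for the 4week and 8 week follow up visits", "then +/- 6months for the 6month and annual visits". It gives no minimum spacing between visits and no rule for assigning an assessment to a nominal time point.

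After radiation, the calendar places toxicity assessment at the follow-up visits. Section 9.3 adds "Adverse event information will be obtained at each contact with the participant". Section 6 says that radiation-related events of grade 2 or above "will be collected from the time of the start of radiation and throughout the study and until the final study visit". Section 9.1, which covers adverse events in general, says they are collected "throughout the study, and within 30 days of the last dose of study treatment", with contact continued for ongoing events.

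For analysis, Section 12.2.1 states: "Exact binomial methods will be used to construct 95% confidence intervals for estimating the rates of acute, sub-acute and late toxicities". It defines no assessment time and no date boundary between the three categories. The nearest thing to a boundary is a remark under the CTCAE table in the appendix, which separates late fibrosis from "pneumonitis that is generally seen within 3 months of radiation or combined modality therapy".

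**The concern.** The half-width of the 6-month window equals the visit time itself. Read literally, an assessment just after radiation ends is a valid 6-month visit, and so is one at month 12. A visit at month 9 satisfies both the 6-month and the 12-month time points, and nothing says which it should fill.

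Two things are at stake. First, late skin and reconstruction toxicity are named objectives in Section 1.3, and the schedule meant to observe them can leave the months after the acute phase empty. Findings that come and go, that are mild, or that need an examiner to grade them are the ones most easily missed. Secondly, the primary endpoint counts events within 3 months of radiation. The last early visit can fall well before month 3, and a 6-month visit that has already been used up no longer serves as a look-back soon afterwards.

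**Working it through.** **The plan's own figures.** The documents give no figure that depends on the visit windows. The design figures nearby reproduce and do not depend on this point:
- Early stop at a true rate of 5%: 1 − 0.95^12 − 12 × 0.05 × 0.95^11 = 0.118 (stated 12%).
- Acceptance under the Section 12.1 rule (at most 1 event in 12, then at most 2 in 26): 81.3% at 5% and 20.0% at 15% (stated 81% and 20%).
- Maximum exact 95% half-width at n = 26: 20.1% (stated 20%).

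**Windows.** Inputs are from Section 7, note 1, with 1 month = 30.44 days, so 1 week = 7/30.44 = 0.23 month.

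| Visit | Window | Months after radiation |
|---|---|---|
| 4-week | weeks 1–7 | 0.23–1.61 |
| 8-week | weeks 5–11 | 1.15–2.53 |
| 6-month | 6 ± 6 | 0–12 |
| 12-month | 12 ± 6 | 6–18 |
| 24-month | 24 ± 6 | 18–30 |

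**Overlap.** The 6-month window contains both early windows. Its first 3 of 12 months (a quarter) lie before month 3. Its last 6 of 12 months (half) also belong to the 12-month visit. The later annual windows touch at their ends but do not overlap.

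**Assessments possible in months 3–12.**
- None: 6-month visit before month 3 and 12-month visit in months 12–18.
- Two: for example, months 6 and 11. Two is the maximum, since the 24-month window opens at month 18. It is also what the nominal schedule gives.

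**Longest compliant gap after the 8-week visit**, with the 6-month visit already used by then and the 12-month visit at month 18:
- 8-week visit at week 11: 18 − 2.53 = 15.5 months.
- 8-week visit at week 5: 18 − 1.15 = 16.9 months.

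If visits must follow the listed order and the 6-month visit is as late as month 3, the gap is still 18 − 3 = 15 months.

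**Primary window.** Three months is 13.0 weeks. The 8-week visit falls between week 5 and week 11, so the last 2 to 8 weeks of the window have no required visit. The next required visit may then be as late as month 18, which is 15 months after the window closes.

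**Illustration only.** The documents do not say when visits actually occur. If timing were uniform and independent within windows, no assessment in months 3–12 would have probability 3/12 × 6/12 = 12.5%. A simulation that forces the visits into order gives about 6.5%. Neither is an estimate for this trial.

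**The case against.** A reader might infer that the reported acute, sub-acute and late rates depend on when patients happened to be seen. The documents do not support that, for these reasons:
- Section 12.2.1 plans no rates by visit and no between-visit toxicity comparison, and nothing classifies an event by visit label.
- Section 6 collects related grade 2 or higher events cumulatively, so a later visit can recover an earlier event. Section 11.4 lists hospital records and charts as source documents, and infections, implant complications and unplanned surgery would normally leave such records.
- The sub-acute endpoint is pneumonitis, which Section 6.1 and the appendix place mostly in the first 3 months. A gap in months 3–12 bears little on it.
- Persistent late effects would still be seen at annual visits to five years.
- The only planned analysis of change over time is strain echo at baseline, 4 weeks and 2 months, outside the 6-month window altogether.
- A spurious difference between the sequential cohorts would need visit timing to drift between them. Nothing shows that it did, and Section 12.1.2 has cohorts generally analysed separately.
- Cosmetic data are limited more directly by Section 7, note 4, and the calendar, which make the forms and photography optional.

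Most of this stands, and it narrows the point. It does not remove it. The Section 6 safeguard leaves out grade 1 findings. For resolved or examination-graded findings it rests on recall or records. The 30-day wording in Section 9.1 can be read as a shorter collection period, a separate inconsistency that makes the safeguard less certain. The six-month figure may also be a drafting slip, but the documents do not show this, and compliance is judged on the text as written.

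**Conclusion.** The point holds in a limited form. As written, the 6-month window does not secure an assessment in months 3–12, and it permits a gap of 15.5 to 16.9 months after the 8-week visit. A record labelled as 6-month can come from the acute phase.

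The consequence is weaker ascertainment of transient, grade 1 or examination-graded late skin and reconstruction findings, plus the lack of a guaranteed visit soon after the 3-month primary window. The two-stage operating characteristics and the strain-echo analysis are unaffected.

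These are limits of what the rules allow, not of what happened. The documents give no visit dates, so no bias in any rate can be quantified. The conclusion assumes that the window applies as printed and that no unstated spacing or assignment rule exists.

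**What to change.** **Section 7, note 1.** Set the window for both the 6-month and the 12-month visits to a half-width below 3 months. For example, ±2 months gives months 4–8 and 10–14. State that one visit may not count for two time points. Any half-width h below 3 months keeps these two windows clear of each other and of the 8-week and 24-month windows, and every compliant patient is then seen after month 3 and before month 9. Both windows must change: narrowing only the 6-month window and leaving month 18 as the 12-month limit would still allow a gap of 18 − (6 − h) = 12 + h, almost 15 months. With ±2 months on both, the longest gap between the two visits is 14 − 4 = 10 months.

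**Section 12.2.1.** Classify toxicity and reconstruction events by onset date since the end of radiation, not by visit label. Keep acute, sub-acute and late as separate categories and state the date limits of each. The 3-month remark in the appendix concerns fibrosis and pneumonitis only, so it should not be carried over to skin and reconstruction without saying so.

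**Cost.** Wording only, with no added visits, tests or patients. More visits will be logged as out of window, but their data are still used by actual date. Date-based classification can also be applied to data already collected. The change does not create a visit at month 3, and it leaves the windows from month 24 onward as they are.
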